3.8 Justification of Choice of Study Population

Depressive disorders already emerge in childhood and adolescence, but no pharmacological treatment with antidepressant medication is approved in Switzerland. All prescribed treatments are “off label”. There is some evidence that in particular adolescents respond with an increase in suicidal ideation in the early phase of SSRI treatment. There is a need for novel treatment as the treatment with cognitive behavioural therapy might not always be feasible or sufficiently effective. Omega-3 fatty acids in adults have shown some beneficial effects in MDD, however, so far only small scale RCTs have been performed. Even so meta-analyses have shown moderate effect sizes in adults, results may not be directly transferrable to paediatric MDD given the bigger brain plasticity and the underlying on-going major developmental processes, as described above (see chapter 3.4.3). Therefore, the inclusion of minors is necessary. Participation in the study is preceded by counselling by the treating doctor / psychologist or investigator, during which the minor and its legal representative/parents are informed about the nature and entire course of the study. Age-adjusted patient information sheets for adults and for minors are available. Informed consent will be sought at the same time by the minors themselves and their legal representatives/ parents. The explicit wish of a minor who is capable of forming an opinion and assessing this information to refuse participation will be followed; in such case, the minor can be withdrawn from the study at any time. If a minor subject does not want to participate, they will not be included in the study. This is also explicitly stated in the patient information sheet.

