4.4 Safety Objectives

Our safety objectives are to investigate if Omega-3 fatty acids have an impact on suicidal ideation (in particular because to the reported increased suicidal ideation in association with SSRIs), and is well tolerated in children and adolescents (WH 5a).

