10.5 Follow up of (Serious) Adverse Events

Participants terminating the study (either regularly or prematurely) with

- reported ongoing SAE, or
- any ongoing AEs of laboratory values or of vital signs being beyond the alert limit

will return for a follow-up investigation. This visit will take place up to 30 days after terminating the treatment period. Follow-up information on the outcome will be recorded on the respective AE page in the eCRF. All other information has to be documented in the source documents. Source data has to be available upon request.

In case of participants lost to follow-up, efforts should be made and documented to contact the participant to encourage him/her to continue study participation as scheduled. In case of minor AEs a telephone call to the participants may be acceptable.

All new SAE or pregnancies that the investigators will be notified of within 30 days after discontinuation of study medication have to be reported in appropriate report forms and in the eCRF if required.

Follow-up investigations may also be necessary according to the investigator's medical judgment even if the participant has no AE at the end of the study. However, information related to these investigations does not have to be documented in the eCRF but must be noted in the source documents.

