11.4.5 Safety Analysis

Safety and harms frequency data will be described based on actual treatment received using MedDRA (integrated in SecuTrial®) and the self-report side effect checklist (ASEC). The rate of harm- and suicide-related adverse events (e.g. SIQ-Jr) in each treatment group will be compared using χ^2 and Fisher exact tests, and ORs will be calculated to provide an indicator of relative risk of the active versus the placebo condition.

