6.2 Difference in Proportion of Responders

A two-proportion z-test would require 97 participants per treatment arm to have 80% power to detect a difference in response of 20% (with 60% response in the treatment group and 40% response in the control group) at the 0.05 two-sided significance level. Accounting for a 10% loss to follow-up results in a total sample size of 216 participants.

7 Statistical analyses

Analysis sets The following analysis sets are defined in accordance with the ICH-E9 guidelines:

- The full analysis set (FAS) includes all randomized subjects. The FAS will be used for 'as randomized' evaluation. Only in exceptional cases may subjects be excluded from the FAS. In such cases the reason for exclusion will be justified and documented.
- The safety analysis set includes all randomized subjects receiving at least one dose of randomized treatment. The safety analysis set will be used for 'as treated' evaluation.

Baseline comparability of randomized groups Baseline descriptive variables of participants (including antidepressant use) will be summarized overall and by treatment arm using suitable measures of central tendencies and variability for continuous data (means or medians, SD or IQR) and frequencies and proportions for categorical data. No hypotheses are tested.

The number of participants lost to follow-up, initiating antidepressants, and adhering to the protocol will each be tabulated by treatment arm and visit. Baseline characteristics will also be summarized across the groups of participants completing the trial, lost to follow-up, and initiating antidepressant use.

General statistical considerations Statistical analysis results will generally be presented as point estimates with two-sided 95% confidence intervals. A limited number of analysis results will additionally be reported with p -values, which will be interpreted as indicative of superiority when the value is less than 5% and the estimated treatment contrast favors the omega-3 treatment arm.

Descriptive statistics for all efficacy and safety endpoints will be presented according to treatment arm.

The baseline values are collected at visit 1 (0 weeks), which is the first week after the lead-in phase. Further measurements are taken at visits 2 through 5 at 6, 12, 24, and 36 weeks.

The clinical trials registry number (03167307) will be used as a seed number, if needed.

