where time t is considered a factor (while also investigating possibility of linearizing time effect) and randomized treatment group (intervention) and the interaction between randomized treatment group and time are included as fixed effects. The baseline values of the minimization factors age, gender, and hsCRP, as well as baseline antidepressant use and omega-3 index are included as covariates. The baseline outcome measure is modeled in the response, not as a covariate. The terms b_{i0} , b_{i1} , and b_{s0} represent participant-specific random intercepts and slopes and site-specific random intercepts. The random effects are assumed to be normally distributed and an unstructured covariance matrix will be assumed. The error term $\varepsilon_i(t)$ is assumed to be normally distributed with mean zero and variance σ^2 , independent of the random effects and is independent over time. An overall treatment effect for CDRS-R score at 36 weeks ($\beta_1 + \beta_{11}$) will be reported with a 95% confidence interval and corresponding p -value.

The competing survival models for time to event r (intervention dropout or study dropout) take the form:

$$\lambda_{ir}(t) = \lambda_{0r} \exp\{\gamma_1 \text{intervention} + \alpha_r m_i(t)\}$$

where the cause-specific Cox models include intervention as a time-independent effect and the estimated true trajectory of CDRS-R as a time-varying effect. The parameters α_r measure the strength of association between the longitudinal outcome and risk of the corresponding dropout event.

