7.2.2 Supportive secondary endpoints

Effect endpoints

- **Number of days in the hospital**
- **Outpatient service use**

These endpoints will be described using summary statistics across treatment arm.

Safety endpoints

- **Suicidal ideation** from baseline to week 36 will be modeled jointly by a linear mixed effects model for SIQ-Jr score over time combined with Cox regression for time to intervention and study dropout, analogously to the CDRS-R total score primary outcome model.
- **Serious adverse events** from baseline to week 36 will be tabulated per type and treatment arm using the safety analysis set. If appropriate, the difference in proportion (with 95% confidence interval) will be estimated.

8 Changes to the statistical analyses planned in the protocol

Version	Explanation
IICT submission	First version of study plan
Frontiers protocol	Study protocol after funding review and peer review, addition of concomitant treatment description, addition minimization factor for unit type (in-/outpatient), description of sensitivity analyses to account for antidepressant use
UZH protocol	Refinement of secondary (supportive/exploratory) outcomes and their analyses
Statistical analysis plan	Focusing the analysis plan on measures of efficacy and safety for reporting of primary trial results. Updating method for dealing with informative missingness.

9 References

N. M. Laird and J. H. Ware. Random-effects models for longitudinal data. *Biometrics* 1982; 38:963–74

R J A Little and L Yau. Intent-to-treat analysis for longitudinal studies with drop-outs. *Biometrics* 1999; 52:1324–33.

S Mazumdar and K S Liu and P R Houck and C F Reynolds. Intent-to-treat analysis for longitudinal clinical trials: coping with the challenge of missing values. *Journal of Psychiatric Research* 1999; 33:87–95

Michele L Shaffer and Vernon M Chinchilli. Including multiple imputation in a sensitivity analysis for clinical trials with treatment failures. *Contemporary Clinical Trials* 2007 28:130–137

Ian R. White and C Bamias and P Hardy and S. Pocock and J Warner. Randomized clinical trials with added rescue medication: some approaches to their analysis and interpretation. *Statistics in Medicine* 2001; 20:2995–3008.

R version and packages used to generate this report:

R version: R version 4.0.1 (2020-06-06)

Base packages: stats, graphics, grDevices, utils, datasets, methods, base

Other packages: pwr, readxl, reporttools, xtable, knitr

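### By analogy with the primary model, the SIQ-Jr safety analysis specifies only a week-36 difference, and the SAP is silent on the protocol's arm comparison of suicide-related adverse events, so early or non-serious harm has no pre-specified between-arm estimate.

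*SAP*

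**What the plan says.** SAP 5.2.2 names two safety endpoints: SIQ-Jr, read at baseline and weeks 6, 12, 24 and 36, and the number of SUSARs. SAP 7.2.2 then plans two analyses.

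- SIQ-Jr over time is fitted by a mixed model "combined with Cox regression for time to intervention and study dropout, analogously to the CDRS-R total score primary outcome model". No contrast or time point is given for SIQ-Jr itself. In the model referred to (SAP 7.1), the reported result is "An overall treatment effect for CDRS-R score at 36 weeks", that is β1 + β11, with a 95% confidence interval and p-value. Time "is considered a factor (while also investigating possibility of linearizing time effect"). Participants are censored at the first of antidepressant start or increase, loss to follow-up, consent withdrawal or exit for non-adherence.
- Serious adverse events to week 36 are tabulated by type and arm in the safety analysis set, with a difference in proportions where appropriate.

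Protocol 11.4.5 promises more: "The rate of harm- and suicide-related adverse events (e.g. SIQ-Jr) in each treatment group will be compared", by chi-square and Fisher exact tests with odds ratios. It describes safety data by treatment received.

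Protocol 4.4 sets the ideation objective "in particular because to the reported increased suicidal ideation in association with SSRIs". Protocol 3.8 cites some evidence that "adolescents respond with an increase in suicidal ideation in the early phase of SSRI treatment". WH 5a (Protocol 5.4) predicts no increase in SIQ-Jr.

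**The concern.** The motivating concern is an early one, yet the only treatment effect specified in the model that SIQ-Jr is to follow is at the last visit. A rise at week 6 or 12 that has settled by week 36 does not enter that difference. Children who worsen early and are started on an antidepressant, or leave the study, stop contributing scores.

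An arm comparison of suicide-related events would cover part of that gap, because it does not depend on the score at a given visit. The protocol plans one and the SAP does not carry it over. Suicide-related events not classed as serious then have no specified comparison at all.

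At stake is the basis for WH 5a, the main safety statement about a product proposed as first-line treatment in children. As written, that statement could rest on a late mean from a censored model.

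**Working it through.** The documents state no sample size, power or expected difference for any safety endpoint, so there is no plan figure to reproduce. The check traces what the specified analysis can show.

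**1. Which visits enter the specified contrast.** With time as a factor and treatment-by-time terms, each arm has a free mean at every visit. With complete data (covariates and site effect set aside), the generalised least-squares estimate of those means is the set of observed visit means, whatever the random-effects covariance. The weights of weeks 0, 6, 12, 24 and 36 on β1 + β11 are therefore 0, 0, 0, 0 and 1. A numerical check with two different random-intercept-and-slope covariances gave the same weights. With dropout, earlier scores help to estimate the week-36 mean of those who left, but the target is still week 36.

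**2. What the same model could report.** Taking baseline as the reference visit, the arm differences at weeks 6, 12, 24 and 36 are β1 + β8, β1 + β9, β1 + β10 and β1 + β11. All four are estimable; the SAP commits to the last.

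**3. What linearising time would do.** Assume time linear in weeks and complete data, with random intercept and slope in the same time variable, so that the fit is the least-squares line.

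- Mean time = (0 + 6 + 12 + 24 + 36)/5 = 15.6.
- Sum of squares = 15.6² + 9.6² + 3.6² + 8.4² + 20.4² = 835.2.
- Weight of week 6 on the fitted week-36 value = 1/5 + (36 − 15.6)(6 − 15.6)/835.2 = 0.200 − 0.234 = −0.034.

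An isolated week-6 rise would lower the week-36 estimate slightly, and no separate visit difference would exist. Another time scale would give other weights.

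**4. Who leaves before the first follow-up.** Protocol 6.2 reports 225 randomised, 21 of whom dropped out before the first follow-up. Protocol 6.3.2 reports about 20 who started an antidepressant within the first 6 weeks. The overlap is not stated.

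- Full overlap: 21/225 = 9.3%.
- No overlap: (21 + 20)/225 = 41/225 = 18.2%.

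These participants may give the censored model no scheduled post-baseline score. The counts are pooled over arms and say nothing about imbalance.

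**5. Event analyses side by side.**

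- Protocol 11.4.5: harm- and suicide-related adverse events, not limited to serious ones; arm comparison with odds ratios; safety data by treatment received.
- SAP 5.2.2: number of SUSARs.
- SAP 7.2.2: serious adverse events only; between-arm difference conditional.
- SAP 2 (list of changes) and SAP 8 (table of changes): neither mentions withdrawing the protocol comparison.

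**6. Precision of a restored comparison.** The documents give no event rates. Assume 3% versus 8% up to 10% versus 20%, with 110 per arm (Protocol synopsis). The half-width of a 95% interval for the risk difference is 1.96 × √[p1(1 − p1)/110 + p2(1 − p2)/110].

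- 3% v 8%: 1.96 × 0.0306 = 0.060.
- 10% v 20%: 1.96 × 0.0477 = 0.093.

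That is about 6 to 9 percentage points either way.

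**The case against.** A reader might infer that the SAP restricts SIQ-Jr to week 36. It does not say so. SAP 7.2.2 speaks of scores over time, and the week-36 sentence in SAP 7.1 names CDRS-R. The restriction is inferred from the reference to the primary model. What stands is that week 36 is the only effect specified in the text referred to, and any other visit is left to discretion. The protocol's own score test for WH 5a (11.4.3) names no visit either.

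A reader might infer that early harm would go unreported. The documents do not support that. Protocol 11 promises descriptives by arm and visit, SAP 7 promises them by arm for every safety endpoint, serious suicide-related events would appear in the serious-event table, and the data monitoring committee follows suicide attempts (Protocol 1.8). What is missing is a pre-specified between-arm estimate.

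Omission is also not withdrawal. The SAP describes itself as based on protocol version 6, so Protocol 11.4.5 may still be meant to apply. That ambiguity is itself the reason to reconcile the two.

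The joint model is designed for informative dropout and does not simply ignore those who leave. True, but the correction rests on the assumed link between score and dropout, and it has least data for those with only a baseline score.

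The SAP's p-value rule, under which results are "interpreted as indicative of superiority when the value is less than 5% and the estimated treatment contrast favors the omega-3 treatment arm", might be read as ruling out a finding of harm. It covers a limited number of results; the general form is an estimate with a two-sided interval, where harm would show.

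Finally, the early-phase concern is about SSRIs, and no passage says omega-3 would act early. That limits how likely the problem is, but the protocol itself ties the objective to the SSRI reports.

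**Conclusion.** The point holds in a limited form. If the reference to the primary model is followed as written, the model-based evidence for WH 5a is one week-36 difference. Visits before it carry zero weight with complete data, and scores after antidepressant start or increase or study dropout are not used. Between 9% and 18% of the first 225 randomised may contribute no scheduled post-baseline score to the model. Separately, the protocol's arm comparison of suicide-related adverse events is absent from the SAP without explanation, so non-serious events of this kind have no specified comparison there.

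This rests on reading the week-36 contrast across from CDRS-R to SIQ-Jr, and on two early-departure counts whose overlap is unknown. It does not show that harm exists or would be concealed. A reader might want a power figure for a transient rise, but the documents give no SIQ-Jr effect size or time course. Any such figure would rest on invented inputs, and the 5% rejection rate at week 36 for an effect that has fully faded is only the type I error. This is an inexpensive improvement worth making, not a flaw that undermines the trial.

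**What to change.** In SAP 7.2.2:

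1. Keep time as a factor for SIQ-Jr and report the arm difference with 95% confidence interval at weeks 6, 12, 24 and 36 (β1 + β8 to β1 + β11). Read the four together as estimates for the safety statement. Do not declare harm automatically from one adverse interval: with no true effect and independent visits, that rule would give 1 − 0.975⁴ = 9.6% false harm calls, against 2.5% for a single visit.
2. Restore the Protocol 11.4.5 comparison. In the safety analysis set and by treatment received, tabulate participants with any suicide-related adverse event, serious or not, by arm, with an odds ratio or risk difference and 95% interval. If it was meant to be withdrawn, record that with a reason.
3. Add observed SIQ-Jr by arm and visit, including scores after antidepressant start. Protocol 8.7.2 does not make such a start a withdrawal criterion, so these visits continue.

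Optionally, also list serious events from after the treatment period, since Protocol 10.5 says that those notified "within 30 days after discontinuation of study medication have to be reported".

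The cost is SAP wording and a few tables from data and a model already planned. The reader gets several safety estimates instead of one, and the event estimate will be imprecise. A rise that comes and goes before week 6 would still be visible only through adverse events.

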7.4 Criteria for Withdrawal/ Discontinuation of Participants

Clinicians/ treating doctors/ patients and their relatives can withdraw a patient at any time if they think it is in his best interest. To support clinicians in their decision making at what point a patients shall be withdrawn from the study for safety reasons, we defined following exit criteria.

Reasons to terminate a subject's participation:

- A subject withdraws her/his consent
- Non-compliance with medication (no intake of study medication for more than three out of seven days in two consecutive weeks)
- Daily omega-3 supplementation in addition to study medication (>600 mg combined EPA/DHA per day for more than one week)
- The clinician or investigator considers a subject's continued participation in the study to be unjustifiable on medical grounds (i.e. because of the emergence of another serious medical condition).
- The subject falls below a score of 40 on the Children's Depression Rating Scale at the end of the placebo lead-in phase.
- Acute Suicidality/ overt hostility: Clinicians and research assistants will monitor suicidality/hostility at each visit. If a clinician/ researcher considers the suicidal risk/ hostility as high requiring some sort of clinical action (e.g. a suicide watch plan as an outpatient, or restricted leave as an inpatient because of intense suicidal ideation/hostility), patients shall be withdrawn from the study if the clinician considers a potential connection with the study drug and a SUSAR shall be reported. The number and type of SUSARs will be compared between the treatment groups (active versus placebo).
- Intolerance to the study drug. Life-threatening side effect other than suicidality/ hostility (SUSAR): In case of an unexpected life-threatening side effect (e.g. a severe allergic reaction to one of the ingredients of the study medication), a patient must be withdrawn from the study.
- The development of a major axis one disorder listed under the exclusion criteria (e.g. a first psychotic or manic episode is considered as a serious adverse event).
- Unwanted but not life-threatening adverse events: If the side effect persists, the study medication shall be ceased and the patient discontinued due to lack of tolerability (an important further outcome criteria).

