3.2 Secondary objectives

- To demonstrate the clinically meaningful efficacy of daily EPA-rich Omega-3 relative to placebo as an adjunct to the standard of care (German S3 guidelines) in children and adolescents with pediatric major depressive disorder.
- To compare the safety and tolerability of daily EPA-rich Omega-3 versus placebo as an adjunct to the standard of care (German S3 guidelines) in children and adolescents with pediatric major depressive disorder.

4 Estimands

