5.2.2 Supportive secondary endpoints

Effect endpoints

- Number of days in hospital
- Lower outpatient service use

Safety endpoints

- Suicidal ideation (SIQ-Jr) from baseline to week 36 (measured at baseline, 6, 12, 24, and 36 weeks)
- Number of SUSARs from baseline to week 36

Statistical considerations

6 Sample size determination

The sample size calculations were performed for the primary outcome, as well as closely related secondary outcomes in order to ensure all questions of high interest are sufficiently powered. All calculations assume a parallel two-arm design with a 1:1 randomization ratio.

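### The SAP ends SAE tabulation at week 36 and specifies no tolerability analysis, although the protocol collects SAEs for 30 more days and the SAP sets an objective to compare tolerability

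*SAP*

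**What the plan says.** **SAP.** Section 3.2 sets a secondary objective: "To compare the safety and tolerability of daily EPA-rich Omega-3 versus placebo as an adjunct to the standard of care". Section 5.2.2 lists two safety endpoints, suicidal ideation on the SIQ-Jr and "Number of SUSARs from baseline to week 36". Section 7.2.2 analyses the SIQ-Jr with a joint model like that of the primary outcome. For serious adverse events it says that they "from baseline to week 36 will be tabulated per type and treatment arm using the safety analysis set", with a difference in proportions and 95% CI if appropriate. Section 7, under general considerations, adds: "Descriptive statistics for all efficacy and safety endpoints will be presented according to treatment arm".

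**Protocol.** Section 10 runs AE and SAE collection from consent to the last study procedure and includes a safety follow-up period. Section 10.5 adds: "All new SAE or pregnancies that the investigators will be notified of within 30 days after discontinuation of study medication have to be reported". Section 11.4.5 plans to describe harms by treatment actually received, "using MedDRA (integrated in SecuTrial®) and the self-report side effect checklist (ASEC"). It also plans to compare rates of harm- and suicide-related events between arms by chi-square or Fisher tests with odds ratios, and it states no week-36 limit. Section 7.4 covers side effects that are not life-threatening but persist: study medication is stopped and "the patient discontinued due to lack of tolerability (an important further outcome criteria").

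**The concern.** Two gaps appear when the SAP is read against the protocol. The first is the time window. An SAE notified in the weeks after the last capsule is collected for a patient who completes treatment, but it does not enter the by-arm SAE table.

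The second is content. The SAP promises a tolerability comparison, yet none of its listed endpoints or analyses measures tolerability. Non-serious adverse events, the ASEC and stopping because of intolerance are all absent. In a paediatric trial with good tolerability among its protocol safety objectives (4.4), a statement in the main report that the treatment was well tolerated could then rest on SAE counts and one suicidality scale. Any tolerability table added later could be labelled post hoc.

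**Working it through.** The point depends on no sample size or power figure, so there is no stated number to reproduce. The check is day arithmetic for the window and a comparison of the two documents for the content.

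**Window.** The inputs are 36 weeks of treatment (Protocol 6.1), 30 days after stopping medication (Protocol 10.5) and a table ending at week 36 (SAP 7.2.2).

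- Week 36 is nominally day 36 × 7 = 252.
- For a completer, collection runs to about day 252 + 30 = 282.
- Share of that period outside the table: 30 / 282 = 10.6%. Expressed relative to treatment time, it is 30 / 252 = 11.9%.
- The SAP does not say whether week 36 is a calendar point counted from baseline. If it is, a patient who stops on day *s* has max(0, *s* + 30 − 252) days outside the table. This is zero for *s* ≤ 252 − 30 = 222 (week 222 / 7 = 31.7) and rises to 30 at *s* = 252.

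The loss therefore affects completers and those who stop after about day 222. The 10.6% is a share of calendar time, not of events.

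**Content.** Each item that the protocol collects or plans, against its place in the SAP:

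1. *Non-serious AEs.* Recorded in the eCRF (Protocol 10.2) and described by MedDRA (11.4.5). Not in the SAP.
2. *ASEC.* A 21-item self-report (9.2.3), given at each study visit (9.2.4.1) and described under 11.4.5. Not in the SAP.
3. *Harm- and suicide-related AE rates.* Compared by arm in 11.4.5. The SAP has the SIQ-Jr model but not this comparison. Because that model follows the primary one, follow-up is censored at a new or increased antidepressant or at drop-out (SAP 7.1).
4. *Discontinuation for intolerance.* Called important in Protocol 7.4, and the primary reason is recorded in the eCRF at the drop-out visit (8.5). The SAP defines study drop-out as consent withdrawal, unavailability for visits or removal for non-compliance (section 7, missing data) and pools these as one event (7.1). Intolerance has no category. Protocol 5.2 (WH 2d) compares overall retention only, so neither document compares intolerance exits by arm.
5. *SUSARs and SAEs.* SAP 5.2.2 names SUSARs and 7.2.2 analyses SAEs. SUSARs are a subset of SAEs, so the listed endpoint and the analysed one differ.

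The SAP's general promise of descriptive statistics by arm covers its endpoints. Items 1, 2 and 4 are not endpoints, so it does not reach them.

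**Is the omission documented?** SAP section 2 gives its scope as efficacy and safety and defers only the inflammatory and lipid marker work. Neither the changes listed there nor the table in section 8 mentions removing Protocol 11.4.5.

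**The case against.** A reader might infer that tolerability data will never be compared and that the objective cannot be met. The documents do not support that.

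- The SAP presents itself as adding detail to protocol version 6, and it does not withdraw Protocol 11.4.5. That section still plans description of MedDRA events and the ASEC by treatment received, and tests of harm- and suicide-related events.
- Protocol section 11 also promises descriptive statistics for all data by medication and visit.
- It is not true that SAP safety reporting covers SAEs alone. The SIQ-Jr is modelled by arm, and SUSARs are a listed endpoint with a two-proportion test in Protocol 11.4.3 (WH5a).

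This stands, within limits. For the ASEC and general AEs the protocol promises description, not testing. Protocol 11.4 says that the SAP will describe all planned a priori analyses. Section 11.4.3 has the statisticians work to the SAP and declares other clinical outcome analyses post hoc. An analysis found only in Protocol 11.4.5 is therefore exposed to omission or relabelling.

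A reader might also infer that every SAE in the 30-day period is lost. On a calendar reading of week 36, the whole window of an early stopper lies inside the table. Post-treatment capture is also largely passive: Protocol 10.5 requires a return visit only for an ongoing SAE or for laboratory or vital-sign AEs beyond the alert limit. Thirty days of notification is not equivalent to thirty days of on-trial surveillance. SAEs also reach the IDMC through the annual list (10.4), although that is not an arm comparison.

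Finally, formal interval estimates for each of 21 ASEC items would be a matter of preference and would raise multiplicity. The ASEC measures antidepressant side effects, and the SAP expects about 30% of patients to receive additional antidepressants, more of them on placebo. A raw arm contrast could reflect antidepressant use and flatter omega-3. That objection stands and shapes the fix.

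**Conclusion.** The point holds as a gap in the SAP. Its SAE table omits up to 30 of about 282 days (10.6%) for a completer, less for those who stop between about day 222 and day 252, and nothing for earlier stoppers. This assumes nominal visit timing and week 36 as a calendar cut-off. How many events fall in that period cannot be derived from the documents, and capture there depends mainly on notification.

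The SAP's tolerability objective has no analysis behind it in the SAP, and Protocol 11.4.5 is neither carried over nor listed as changed. Discontinuation for intolerance has no by-arm comparison in either document. The primary efficacy result is not affected; what is at stake is whether the safety and tolerability statements in the main report rest on pre-specified tables.

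**What to change.** In SAP 5.2.2 and 7.2.2:

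- Set the SAE window from first randomised dose to 30 days after last dose, with a footnote that post-treatment events rest on notification.
- Carry over Protocol 11.4.5, including its comparison of harm- and suicide-related events. Summarise all AEs by MedDRA term and the ASEC descriptively by arm in the safety analysis set. Show the ASEC also by antidepressant use, noting that this is a post-randomisation split and not a randomised comparison.
- Add discontinuation for intolerance by arm, with a risk difference and 95% CI, from the reason for discontinuation in the eCRF.
- Reconcile SUSARs in 5.2.2 with SAEs in 7.2.2, so that the listed endpoint is the analysed one.

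The cost is SAP text and a few more tables. AEs, the ASEC and exit reasons are already collected, and the as-treated safety set is already defined. The drawback is sparser capture after week 36, which the footnote makes visible.
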